The purpose of this Window of Opportunity study is to identify the molecular and genetic mechanisms by which statins influence breast cancer cell proliferation. Preclinical data suggest that statins, the most commonly used cholesterol-lowering medication, may influence mammary cancer growth, but the clinical evidence is inconsistent. Epidemiologic studies suggest that prior statin intake may be associated with earlier stage breast cancer at diagnosis, lower risk of relapse and lower breast cancer mortality rates. Our study sample will include women with newly diagnosed clinical stage 0 (insitu) and stage I and II, invasive breast cancer who will be treated with simvastatin (20 mg) for 2 to 4 weeks in the window of time between their initial breast cancer diagnosis until the time of definitive breast surgery. Left-over breast tumor tissue from both the diagnostic and surgical specimens will be obtained for analysis. The primary study endpoint will be change in expression from pre- to post—treatment of tissue levels of ki-67, a marker of breast tumor proliferation. Secondary endpoints will include changes in other candidate predictive markers of breast tumor proliferation which will include cyclin D1 and P27; as well as changes in markers of apoptosis (cleaved caspase-3 (CC3)); inflammation (c-reactive protein (CRP)), composition of the plasma membrane (lipid rafts) as well as tumor-specific CYP27A1 expression. We will also measure changes in tumor signaling molecules that may be also altered by cholesterol depletion including estrogen receptor (ER), progesterone receptor (PR) and HER2neu as well as any changes in tumor grade. Since the primary effect of statins includes the inhibition of hydroxymethylglutaryl CoA reductase (HMG-CoA), we will evaluate the effect of statins on cell proliferation and apoptosis based on tumor expression of HMG- CoA. As a pilot analysis we will compare the effect of statins on breast tumor proliferation and apoptosis between groups defined by tumor expression of ER, PR status, HER2neu and histologic grade. This study will add to the field by confirming the results of two prior window of opportunity studies in similar patient populations. We will in addition, add new biomarkers previously not explored in this clinical situation including composition of the plasma membrane (lipid rafts) and activation of signaling markers (pAkt, pMAPK, pEGFR, pHER2).

Study Schema

Study Glossary

Definitions

TABLE OF CONTENTS

1. OBJECTIVES
2. BACKGROUND AND RATIONALE
3. EXPERIMENTAL PLAN
4. SUBJECT ELIGIBILITY
5. SUBJECT ENROLLMENT
6. TREATMENT PROCEDURES
7. STUDY PROCEDURES
8. REMOVAL AND REPLACEMENT OF SUBJECTS
9. SAFETY DATA COLLECTION, RECORDING, AND REPORTING
10. STATISTICAL CONSIDERATIONS
11. ADVERSE EVENTS
12. REFERENCE

1) OBJECTIVES

- a) Evaluate the relationship between short-term use of oral simvastatin on change in expression of Ki-67 as a candidate biomarker of breast tumor proliferation among women with clinical stage 0 insitu and 1 or 2- primary invasive breast cancer.
- b) Evaluate the relationship between short-term use of oral simvastatin on changes in other candidate predictive markers of breast tumor proliferation (cyclin D1 and P27), changes in a marker of apoptosis (cleaved caspase-3 (CC3), changes in a marker of inflammation (c-reactive protein (CRP), novel additional biomarker changes in the composition of the plasma membrane (lipid rafts), changes in .activation of signaling markers (pAkt, pMAPK, pEGFR, PHER2) and changes in serum levels of 27-hydroxycholesterol (27OHC) and tumor expression of CYP27A1.
- c) To conduct exploratory analyses comparing the effect of statins on breast tumor proliferation and apoptosis in groups defined by tumor expression of hydroxymethylglutaryl CoA reductase (HMG-CoA), ER/PR status, HER2neu, and tumor grade.

2) BACKGROUND AND RATIONALE

- a. **Introduction:** Statins are a class of medications that are competitive inhibitors of Hydroxy Methyl Glutaryl Co-enzyme A (HMG-CoA) reductase which is the rate-limiting enzyme in the cholesterol bio-synthesis pathway. As a result, statins lower total (TC) and low density lipoprotein cholesterol (LDL-C) and have a favorable impact on cardiovascular mortality (1). The downstream effects of statins are not limited to inhibition of cholesterol synthesis alone. Statins have anti-inflammatory effects thought to be important in the setting of acute myocardial infarction which also may be a mechanism involved in anti-carcinogenic properties of statins (2). Furthermore, statin inhibition of the mevalonate pathway may impact Ras and RhoGTPases which are important in cell proliferation, migration and apoptosis and as such support a role for the anti-cancer effects of statins (3-6). All of the alterations associated with statins may play a role in the anti-cancer effect of statins.

Statins are chemically classified based on their solubility into octanol soluble (lipophilic) or water soluble (hydrophilic). Lipophilic statins (lovastatin, simvastatin, fluvastatin) penetrate the plasma membrane and are reported to interrupt mevalonate synthesis both in the liver and periphery while hydrophilic statins (pravastatin and atorvastatin) are taken up only by active transport and only affect selected hepatocytes that have transporter molecules (7) . Reports in the literature suggest a differential effect of statins on cancer prevention based on the type or class of statin (8-11). It is postulated that the cellular uptake of lipophilic statins may be related to their inhibition of cell growth. This concept is supported by a cell culture study in which only lipophilic statins were shown to have anti-cancer activity (10).

- b. Epidemiologic Studies:** Population based studies of the association between statins and cancer risk have demonstrated mixed results with some studies showing a protective effect for some cancers (12-15) and other studies showing an increased cancer risk or no association (16-19). Two meta-analyses evaluated the effect of statins on breast cancer risk, one of which included 7 randomized trials and 9 observational studies (20) and the other, 7 randomized trials (21) and both showed no significant association. A recent prospective cohort analysis showed no significant relationship between prior statin use and colon, lung, pancreatic, breast or bladder cancer however there was a reduction in risk of melanoma, endometrial cancer and NHL (22). Another nested case control study revealed an increased risk of bladder, colon and lung cancer associated with past statin use, however a reduced risk of hematological malignancies including myeloma, leukemia and lymphoma (23). In a meta-analysis of twenty case control studies, there was a protective effect for colon cancer, but no effect on breast, lung and prostate cancer risk (24). Other studies have demonstrated a protective effect of statins including a US veteran's study which demonstrated a reduced risk of pancreatic cancer (25) and three recently completed meta-analyses showed a reduced risk of colon cancer (26-28). While the results of epidemiological studies of statins and cancer risk are conflicting, other studies looking at the relationship between statins and breast cancer outcome suggest a possible protective effect showing a relationship between prior statins and earlier stage at diagnosis (29;30), lower rates of relapse (31-33) and lower breast cancer mortality (30;34;35).
- c. The effect of statins on breast tumor proliferation, apoptosis and cell-cycle regulation:** A number of preclinical findings support the biologic plausibility of a protective effect for statins in relationship to the development of breast cancer. Statins act by inhibition of HMG-CoA reductase (HMG-CoAR) and have pleomorphic properties in the cell. In-vitro data has shown anti-proliferative, apoptotic and anti-invasive properties of statins in cancer cell line studies (36-41). In vitro studies of breast and lung cancer cell lines have reported statin induced decrease in expression of anti-apoptotic BCL-2 and increase in pro-apoptotic BAX protein (42). It has been postulated that a change in the balance of pro-and anti-apoptotic signals toward the former may enhance the apoptotic activity of chemotherapy.

Another possible chemo preventive activity of statins may be related to statin induced inhibition of the mevalonate pathway (5;38;43;44). Farnesyl diphosphate (FPP) and geranylgeranyl diphosphate (GGPP), downstream products of the mevalonate pathway, are both involved in posttranslational modification of many proteins such as the Ras molecule (45), which in turn helps transmit downstream signaling from surface receptors (46). Ras is involved in many intracellular pathways and increases gene transcription and proliferation by acting through the MEK and phosphoinositide 3-kinase (PI3K)/Akt pathways (36). Inhibition of this pathway can have anti-proliferative effects on cancer cells (37).

Statins have also been implicated in reducing cell migration, proliferation, and invasion by inhibiting production of GGPP, which is involved in geranylgeranylation of Rho proteins including Rho GTPases (38) that maintain function of Rho kinases involved in various cellular functions including gene expression, actin cytoskeleton migration, adhesion, and contractility of cells (47). Preclinical studies have demonstrated that statin treatment alters the composition of the plasma membrane. By reducing overall cholesterol concentrations, membrane structures referred to as lipid rafts are disassembled and key growth factor receptors are un-clustered. Several groups have demonstrated an increase in sensitivity to tyrosine kinases inhibitors, including EGFR and HER2 inhibitors, in the presence of statins (1-3).

In a pre-operative study of women with stage 0 and 1 breast cancer, fluvastatin (80 mg vs. 20 mg) was administered for 3-6 weeks between the time of initial diagnosis and up until the time of the definitive breast cancer surgery. Statin use was associated with a reduction in breast tumor proliferation (7.2% reduction in Ki-67 expression in high grade tumors vs 0.3% reduction in low grade tumors) and a preferential increase in tumor apoptosis in high-grade vs. low-grade tumors (60% vs. 13%) as well as ER-negative vs. ER-positive tumors (55% vs 28%) (48). In a similar study of atorvastatin 80mg administered for 2 weeks among women with stage I and II invasive breast cancer, there was a 7.6% reduction in Ki67 expression with a higher reduction of 68% noted among breast tumor samples that had high expression of HMGCoAR (49).

Other studies have focused on molecular explanations of the effect of statins In a study of murine xenografts, simvastatin stimulated production of a variant of the p53 transcription factor and diminished the potential to form bone metastases (50). Other evidence also implicates the p53 pathway. A 3-dimensional breast cancer cell culture model showed that mutant p53 up-regulated the mevalonate pathway to induce an invasive phenotype. Addition of simvastatin to the culture medium caused reversion to normal morphology, while the malignant phenotype persisted when both simvastatin and GGPP were present in the medium (51).

Borgquist et al suggested that the antiproliferative action of statins is due to an effect on cyclin D1 and p27, through up-regulated expression of the tumor suppressor p27 and down-regulated expression of the oncogene cyclin D1 in breast cancer. (52). In normal cells, progression through the cell cycle is controlled by the cyclin dependent kinases (CDKs), a family of serine/threonine kinases (53). The CDKs form complexes with their regulatory units, cyclins, thereby activating the CDKs, leading to phosphorylation of the cell cycle regulatory proteins that initiate and regulate progression through the different phases of the cell cycle (54). In breast cancer cells, the cell cycle control system is deregulated at multiple levels, leading to abnormal cell proliferation (55). Cyclin D1 is a vital regulator of the G1/S transition. The interaction of cyclin D1 with CDK4 and CDK6, leads to phosphorylation and thereby inactivation of the Rb-protein and its G1-maintaining

function, which culminates in the expression of proliferation-associated target genes (56;57). Cyclin D1 is overexpressed at the protein level in up to 50% of all primary breast cancers, in part due to amplification of the cyclin D1 gene, CCND1 (58). The CDK inhibitor p27, also known as Kip1, is involved in the regulation of the G0-to-S-phase transition. p27 interacts with CDK2-cyclin E, CDK4/6-cyclin D, and CDK2-cyclin A complexes, thereby strictly regulating these complexes (59;60). The tumor suppressor p27 is frequently deregulated in breast cancer, and reduced p27 expression has been associated with increased proliferation, high tumor grade, HER2 amplification as well as estrogen receptor (ER) and progesterone receptor (PR) negativity. Feldt and colleagues showed that following statin treatment that cyclin D1 expression was significantly decreased and that the protein expression of the tumor suppressor p27 increased significantly (52).

- d. Impact of 27-hydroxycholesterol in breast cancer development: 27-hydroxycholesterol (27OHC), is the most prevalent oxysterol (38;39)(40), and is a primary metabolite of cholesterol. 27OHC is generated enzymatically by the P450 enzyme sterol 27-hydroxylase (CYP27A1) which is present in the liver, intestine, vasculature, brain as well as macrophages (39) and catabolized by 7-alpha hydroxylase CYP7B1, which is abundant in the liver (38;39;41). 27OHC functions as a naturally occurring ER ligand and acts as an in-vivo SERM that exhibits ER-agonist activity (42;43) demonstrated by its induction of a unique active conformation of ER alpha (42;43). Oxysterols also serve multiple roles in lipid metabolism (38;44), and function as ligands for the liver X receptor (LXR) alpha and beta (45). Results from cell culture and mouse models have led investigators to hypothesize that the relationship between obesity, high cholesterol and breast cancer is modulated through the action of endogenous 27OHC (24;40;46-48), and that endogenous production of 27OHC is in part responsible for acquired resistance to Tamoxifen (49) and AI's (36).

With the identification of 27OHC as an endogenous SERM, studies have evaluated its potential activity on ER positive breast cancer cell lines. In a series of experiments, 27OHC has been shown to upregulate ER alpha, increase cyclin D1 expression, increase the number of cells entering S phase, and increase overall cell number (50). Wu et al (51) and others (47) reported that 27-OHC stimulates MCF-7 cell xenograft growth in mice. Wu also showed that 27OHC is produced by MCF-7 cells, and stimulates cell-autonomous, ER-dependent and GDNF-RET-dependent cell proliferation concluding that 27OHC is a locally-modulated, non-aromatized ER ligand that promotes ER sensitive breast tumor growth. He also demonstrated that diminished expression of CYP7B1 (enzyme responsible for 27OHC metabolism) is associated with higher levels of 27OHC.

In another series of experiments, Nelson et al (24) demonstrated that 27OHC increases the growth of ER-positive breast cancer, and that the genetic or pharmacologic inhibition of 27OHC attenuates hypercholesterolemia-promoted tumor growth. Other mouse experiments demonstrated that elevated 27OHC was associated with increased frequency of lung metastases (24). In a series of studies using aggressive human breast cancer cell models, Nelson identified high levels of CYP27A1 (enzyme which converts cholesterol to 27OHC), suggesting that intra-tumoral 27OHC production may play a role in carcinogenesis. In a study of AI-resistant breast cancer cell lines, Nguyen found that active cholesterol biosynthesis sparks the activation of ER alpha, partly by the synthesis of 27OHC (36). Raza, et al investigated the extent to which 27OHC regulates cell proliferation in MCF7 - ER-positive breast cancer cell lines and found that treatment of MCF7 cells with 27OHC resulted in reduced p53 transcriptional activity, and was associated with increased levels of the E3 ubiquitin protein ligase MDM2, and decreased P53 levels (47).

In the only reported study of 27OHC in women with breast cancer, Wu et al (51) measured serum 27OHC in a sample of 66 breast cancer cases and 18 age and race-matched controls. While the results showed that mean 27OHC serum levels were similar for cases and controls (approximately 120 ng/ml), mean levels in 10 cases were more than 2SD's above that of controls, suggesting some variability among affected women with breast cancer. It is unclear whether the heterogeneity in these results reflects a true biologic difference possibly related to tumor burden, or whether the differences are only due to chance. In his study, Wu et al also compared levels of 27OHC in normal and tumor tissue and normal tissue in controls and demonstrated a 3-fold higher level of 27OHC in normal tissue from cases compared to controls with further enhancement of 27OHC in breast tumors. They found no observed association between serum and tumor 27OHC (51).

To evaluate the relationship between 27OHC and coronary heart disease (CHD), Rossouw et al, used a nested case-control design and archived serum samples from 350 women with CHD and 813 matched controls from the WHI Hormone Therapy trial (52). 27OHC levels were analyzed at the Atherosclerosis Research Lab at the Baylor College of Medicine, using a modified isotope-dilution gas chromatography-mass spectrometry method (53). There were no noted differences in 27OHC levels in cases vs. controls (36.5 nmol/L vs 37.7 respectively) however 27OHC was significantly correlated with high density lipoprotein cholesterol (HDL), low density lipoprotein cholesterol (LDL) and total cholesterol (TC). For each 10% increase in serum 27OHC, there was a significant 8% decrease in HDL and a significant 14% and 18% increase in LDL and TC, respectively. 27OHC was inversely correlated with BMI

in this study. Finally 27OHC was not independently associated with risk of CHD, nor did it modify the relationship between hormone therapy and CHD risk.

We have utilized Women's Health Initiative (WHI) data to study the relationship between statins and: cancer risk (54-58); breast cancer stage at diagnosis and mortality (59) and overall cancer mortality (60). Whereas our results suggest a very modest chemo-protective role for statins (54;56;58) we demonstrated that statins may be associated with better breast cancer survival (59), a result which has also been replicated by others (61-63). We hypothesize that one possible mechanism for the protective role of statins is through the reduction in circulating levels of cholesterol, resulting in lower levels of 27OHC and/or intratumoral levels of CYP27A1. If true, this would suggest that 27OHC may be a modifiable risk factor for breast cancer (40;49;64).

- e. **Summary:** Epidemiologic and laboratory studies suggest that statins may have a favorable impact on clinical outcomes among women with breast cancer, however there have only been two published window of opportunity (perioperative) studies which have directly evaluated the effect of statins on markers of breast cancer proliferation, apoptosis and cell cycle regulation (48;49). We propose to further replicate the findings of these studies which suggest that a short course of pre-surgical statins may have a favorable impact on markers of breast cancer prognosis. We will also conduct exploratory analyses comparing the effects of statins on breast tumor proliferation stratified by tumor expression of HMG-CoA, ER/PR status, HER2neu and tumor grade. We will use a "window-of-opportunity" mechanism to explore the effects of statins on women with clinical stage 0 insitu and I or II early stage invasive breast cancer in the short period of time between initial diagnosis and definitive breast surgery. Statins are widely accepted as treatment for high cholesterol and treatment for atherosclerotic heart disease, and associated with minimal toxicity, and if shown to have a favorable effect on markers of breast tumor growth, have the potential to lower the risk of long-term breast cancer and cardiovascular morbidity and mortality.

3. EXPERIMENTAL PLAN

We will use a phase II "window of opportunity" design in which women with clinical stage 0 insitu or stage I or II invasive breast cancer will be enrolled during the time period between their definitive breast cancer diagnosis after core needle biopsy and the final surgical removal of their tumor. At the Karmanos Cancer Center (KCC), the majority of women with newly diagnosed stage 0 insitu and stage I and II invasive breast cancer are evaluated in the Walt Multidisciplinary Breast Clinic at the Detroit campus of the KCC or at the Weisberg cancer treatment center in Farmington Hills, MI. The majority of women with newly diagnosed breast cancer are scheduled for definitive

surgical resection within approximately 4 weeks of their initial diagnosis. All participants in this window of opportunity study will be provided a dose of simvastatin 20 mg for at least 2 weeks and no longer than 4 weeks in the interval between biopsy and definitive surgery. Simvastatin is one of the most commonly prescribed statins and is a lipophilic, high-potency statin, making it a reasonable candidate statin for this study. Simvastatin will be provided free of charge to the participants by the investigator through the KCI pharmacy. We will analyze both pre- and post-treatment biopsy/tumor specimens for markers of breast tumor proliferation, apoptosis, cholesterol metabolism, cell signaling and intra-tumoral expression of CYP27A1 and will analyze tumors as well for standard markers of breast cancer prognosis (ER, PR, HER2neu and tumor grade). This study will be conducted at the KCC (Walt Center and Weisberg and other Network Centers including Flint and Bay City) as well as Ascension Providence Hospital and the Henry Ford Health Systems as the clinical sites. As part of the protocol we will collect pre and post-surgical blood specimens to measure serum levels of total cholesterol (TC), high density lipoprotein cholesterol (HDL-C), low-density lipoprotein cholesterol (LDL-C) and 27-hydroxycholesterol (27OHC). The pre-surgical blood specimen will be obtained at the screening visit and the post-surgical blood specimen will be collected up until the first post-operative visit.

4. SUBJECT ELIGIBILITY:

a. Inclusion Criteria

- i. Provision of informed consent prior to any study specific procedures.
- ii. Female patients must be > 18 years of age.
- iii. Histologic confirmation of insitu or invasive breast cancer with any measures of ER, PR and HER2neu.
- iv. Clinical stage 0, I or II breast cancer for which there will be at least a 2 week period of time between diagnosis and definitive surgery.
- v. Performance Status (EGOG 0-2).
- vi. Not currently pregnant during the study. Participants will be informed that the use of contraceptive pills is contraindicated because it may interfere with the study drug and it may be harmful to the woman who has been diagnosed with breast cancer.

b. Exclusion criteria

- a. Plans for administration of neoadjuvant chemotherapy or hormonal therapy.
- b. Previous or concurrent malignancy (with the exception of non-melanomatous skin cancer) within 1- year of the date of the consent.
- c. Severe gastrointestinal disorder.
- d. Current use of statins or fibrates for any time during the 3 months prior to the study.
- e. Proven hypersensitivity to statins.

- f. Mild or higher alterations of hematologic, liver and renal function. (i.e., WBC <2,500 /mm³, Plt <100,000/mm³, HgB <8 g/dL, AST >45 U/L, ALT >45 U/L, creatinin >1.5 mg/dL, bilirubin >1.15 mg/dL and CPK > 250 mg/dL);
- g. CNS diseases and major psychiatric diseases or inability to comply to the protocol procedures;
- h. Active infections;
- i. Cardiac failure, class I-IV;
- j. Current treatment with coumadin.
- k. Mitral and/or tricuspid valvulopathy or valvular prosthesis; Angina; Severe arterial hypertension;
- l. Current lactation.

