6. TREATMENT PROCEDURES

- a. Simvastatin will be obtained from commercial sources and will be provided free of charge to the participant through the KCI pharmacy. Participants will take simvastatin 20 mg daily for at least 2 weeks and no longer than 4 weeks, from the time of consent to the day prior to their definitive breast surgery. A pill diary will be maintained through the clinical trials office.
- b. Serum total cholesterol (TC), low-density-lipoprotein cholesterol (LDL-C) and high density lipoprotein cholesterol (HDL-C) will be measured in the KCI tissue core lab (PI [name]) at study entry, and at the end of statin administration. Pathology slides and tissue block material will be obtained from clinical pathologic material not needed for clinical purposes from the biopsy specimen and lumpectomy or mastectomy specimen.
- c. Participants will be monitored for toxicity through telephone monitoring and clinic visits as needed. Telephone monitoring will occur 3-5 days after initiating simvastatin and within 2 weeks of stopping simvastatin. Details about reported side effects will be maintained by the study nurse.
- d. Participants will be provided a \$25 Target gift card after the completion of all study related activities.

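### Section 3 places the second serum sample after surgery and after the last simvastatin dose, so the 27OHC change cannot be separated from an effect of the operation

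*Combined protocol and SAP*

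**What the plan says.** **Section 3 (Experimental Plan)** provides two blood samples for TC, HDL-C, LDL-C and 27OHC. On the first: "The pre-surgical blood specimen will be obtained at the screening visit". It is called pre-surgical, but it is in fact the pre-treatment baseline. On the second: "the post-surgical blood specimen will be collected up until the first post-operative visit".

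**Section 6a (Treatment Procedures)** has women take simvastatin "from the time of consent to the day prior to their definitive breast surgery". It adds: "A pill diary will be maintained through the clinical trials office".

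**Section 6b** says that TC, LDL-C and HDL-C are measured "at study entry, and at the end of statin administration". It does not list 27OHC.

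**Section 1, objective (b)** includes "changes in serum levels of 27-hydroxycholesterol (27OHC) and tumor expression of CYP27A1". The three lipids appear in no objective. Serum 27OHC is in the Section 7 list of serum markers, but it is not among the endpoints named in the opening summary or in Section 11.

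**Section 2d** gives the reason for the serum work. One possible mechanism for a statin benefit is a "reduction in circulating levels of cholesterol, resulting in lower levels of 27OHC and/or intratumoral levels of CYP27A1".

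**The concern.** The serum markers are there to show what simvastatin does to circulating cholesterol and 27OHC. That calls for a sample taken while the drug is acting, or immediately at the end of the course. Section 3 instead puts the second sample after both the last dose and the operation, with only a latest time and no fixed day.

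Two things then come between the drug and the measurement: days off drug, and the surgery itself. There is no control arm, and no woman has a follow-up sample taken before her operation, so nothing in the data shows what the operation alone does to these markers. A small 27OHC change could mean no drug effect or a late draw. A clear change could come partly from surgery. The serum part of the Section 2d hypothesis would stay unresolved either way, and once a woman has had surgery her end-of-treatment sample cannot be recovered.

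Sites also have two instructions for the same lipid measurement, one in Section 3 and one in Section 6b.

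**Working it through.** The documents state no figure for this point, so the check sets the timing statements side by side.

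**1. Timeline.** Call the day of surgery day 0.
- Last dose (Section 6a): day −1.
- Second draw (Section 3): day k, with k ≥ 0 because the sample is post-surgical. The upper limit is the first post-operative visit, whose day the available text does not give.
- Days off drug at the draw = k − (−1) = k + 1.
- Days since surgery at the draw = k.

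Even the earliest draw, k = 0, follows both the last dose and the operation.

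**2. What the change measures.** Write the mean observed change as

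observed = r(k + 1) × D + S(k) + E,

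where D is the change present at the end of treatment, r the fraction of it left after k + 1 days off drug, S the shift due to surgery, and E any other change over time. The aim is D. Under Section 3, r may be below 1 and S is present in every woman. A sample at the end of treatment and before surgery has r = 1 and S = 0, which leaves D + E. E remains in any single-arm design and is not part of this point.

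**3. Whether analysis could repair it.** For every woman who follows Section 6a, days off drug and days since surgery differ by the same constant: (k + 1) − k = 1. A regression on days since last dose would describe the two influences together and could not tell them apart. No section provides for recording the interval or using it, although the pill diary should give the last-dose date.

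**4. Section 3 against Section 6b.** For the lipids, 6b's timing and Section 3's post-surgical draw agree only when k is very small. At k = 0 the draw is one day after the last dose, which can loosely be called the end of the course. At a later post-operative visit the two do not agree. For 27OHC there is nothing in 6b to compare with.

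**5. What is affected.** Serum TC, LDL-C, HDL-C and 27OHC. Ki-67 and CYP27A1 are measured on biopsy and surgical tissue (Sections 5 and 7) and do not depend on the blood draw.

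**6. Size.** The documents give no expected serum change, no variability of that change, no rate at which lipids or 27OHC return after stopping, and no effect of surgery on them. D, r and S are all unknown, so neither the amount nor the sign of the bias can be computed.

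**The case against.** **Section 3 sets only a latest time.** A draw on the day of surgery, after the operation, would satisfy Section 3 and arguably 6b, which does not say that the lipids must be measured before surgery. This stands: a reader might infer that the two sections flatly contradict each other, and the wording does not go that far. But nothing limits the draw to that day, and even a same-day draw follows the operation.

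**The schema is not shown.** It might date the post-operative visit. This also stands. A date would cap the interval, but it would not move a post-surgical sample to before surgery.

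**Section 11 times the second biomarker assessment shortly before the operation.** A reader might infer that this contradicts Section 3 for 27OHC as well. The sentence names no serum marker, the endpoints and analyses around it concern Ki-67 and stained tissue markers, and the second tissue sample is itself taken at surgery. It is indirect support at most.

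**The markers are secondary.** The lipids are in no objective, serum 27OHC is not a named endpoint, and the CYP27A1 half of the hypothesis is tested on tissue. All true, and this limits the weight of the point. Serum 27OHC change is still in objective (b).

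**The post-operative visit may have been chosen for feasibility.** Section 6c plans telephone contacts, with clinic visits only as needed, so a pre-operative draw is an extra thing to arrange. That is a real cost and is counted as one in the fix.

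**Conclusion.** The concern holds for the serum markers. As Section 3 is written, the serum 27OHC change in objective (b) cannot be separated from an effect of surgery and may be diluted by a varying time off drug. For the lipids, Sections 3 and 6b are consistent only if blood is drawn very soon after surgery.

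A reader might go further and infer a stated loss of power or rise in false positives. The documents do not support one. The effect sizes in Table 1 were set for Ki-67, and the 1% level was set for the sample size calculation; any retained fraction or surgery shift would be pure assumption. Early draws may lose little. Nor does the point touch the primary endpoint or tumor CYP27A1.

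The conclusion rests on reading the post-surgical label literally, on women stopping simvastatin when Section 6a says, and on the available text without the schema. It should be settled before samples are collected.

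**What to change.** Reconcile Sections 3 and 6b to one serum sampling time for TC, LDL-C, HDL-C and 27OHC: at the end of treatment and before surgery. State the permitted window, and name the serum markers wherever Section 11 describes assessment times. Record the dates of last dose, surgery and draw. If post-surgical samples are also taken, or are all that can be obtained from some women, analyse them separately as off-treatment samples and report days since last dose.

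Cost: the protocol change is one of wording, and the number of draws does not rise. The draw date is the main new data item, since the last-dose and surgery dates should be obtainable from the pill diary and source records. The practical burden is that several sites must arrange a research draw before surgery instead of using a post-operative visit. Whether an existing pre-operative draw could serve is an assumption that the documents do not settle. Some samples may be missed, and those women would drop out of the on-treatment serum analysis.
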